10.3 POPULATIONS FOR ANALYSIS

Intention to treat: any subjects who enroll onto the trial and provide consent and who receive at least one dose of either agent will be included in the safety evaluations, and those who receive a least one dose of both agents will be included in the efficacy evaluations.

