3 STUDY IMPLEMENTATION

3.1 STUDY DESIGN

The proposed study is an open label, single-arm phase II study of VB-111 in combination with anti-PD1, nivolumab, in patients with advanced, refractory CRC.

Treatment will be delivered in cycles consisting of 2 weeks (+/- 3 days).

VB-111 will be administered every 6 weeks starting on cycle 1 day 1 and nivolumab will be administered every 2 weeks starting on cycle 2 day 1 ([Schema 1](#) and [Table 5](#)).

[figure not shown]
Treatment will continue until off treatment criteria are met (see Section [3.7.1](#))

If one of the study drugs is permanently discontinued because of toxicity, the patient may continue the other study drug per PI discretion until off treatment criteria are met (Section [3.7.1](#)).

Patients will be monitored every 8 (+/- 1) weeks with imaging.

Treatment will be delivered without planned hospitalization. Admission for logistical reasons is allowed (i.e. if patients cannot travel home the same day or biopsies are scheduled etc.)

Patients will have two mandatory research biopsies: at baseline and either day 1 of cycle 2 (post VB-111 but pre-checkpoint inhibitor treatment) or day 1 of cycle 4 (post-VB-111 and checkpoint inhibitor treatments). Timing of the research biopsy will be determined in an alternating fashion by the research team on a 1:1 basis; i.e. the team will assign patient #1 to early second biopsy (day 1 of cycle 2), patient #2 to late second biopsy (day 1 of cycle 4) and so on.

Schema 1: Study design. Patients will undergo pre-treatment biopsy and one post-treatment biopsy at Day 1 of Cycle 2 or Day 1 of Cycle 4.

Table 5: Treatment regimen

VB-111, every 6 weeks	Nivolumab, every 2 weeks
1x10 ¹³ VP IV (for patients with weight ≥ 50kg)	240 mg IV
0.7x10 ¹³ VP IV (for patients with weight > 35kg and <50 kg)	

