10 STATISTICAL CONSIDERATIONS

10.1 OBJECTIVES

Primary:

- To determine the safety and tolerability of VB-111 in combination with nivolumab in patients with refractory, metastatic CRC.
- To determine Best Overall Response (BOR) (PR+CR) according to Response Evaluation Criteria (RECIST v1.1) of combined treatment of VB-111 and nivolumab in patients with refractory, metastatic CRC.

Secondary:

- To evaluate a 6-month progression-free survival.
- To evaluate progression-free survival.
- To evaluate overall survival

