10.2 SAMPLE SIZE DETERMINATION

The safety and tolerability will be evaluated on all patients who receive at least one dose of both agents; the sample size will be determined by the efficacy endpoint.

Based on previous experience, patients with mCRC who have failed other treatments are unlikely to experience a clinical response to a single agent. However, it would be desirable if the response rate could exceed 10% in patients who are treated with this combination. This trial will be conducted using a Simon optimal two-stage phase II trial design (Simon R, Controlled Clinical Trials 10:1-10, 1989) to rule out an unacceptably low response rate (CR+PR) of 5% ($p_0=0.05$) in favor of an improved response rate of 25% ($p_1=0.25$). With $\alpha=0.10$ (probability of accepting a poor treatment=0.10) and $\beta = 0.10$ (probability of rejecting a good treatment=0.10), the first stage will enroll 9 evaluable patients, and if 0 of the 9 has a response, then no further patients will be accrued. If 1 or more of the first 9 patients have a response, then accrual would continue until

a total of 24 evaluable patients have been treated. As it may take up to several months to determine if a patient has experienced a response, a temporary pause in the accrual may be necessary to ensure that enrollment to the second stage is warranted. If there are 1-2 patients with a response out of 24 patients, this would be an uninterestingly low response rate. If there were 3 or more of 24 (12.5%) who experienced a response, this would be sufficiently interesting to warrant further study in later trials. Under the null hypothesis (5% response rate), the probability of early termination is 63.0%.

It is expected that 2.5 years may be required to enroll up to 24 evaluable patients. To allow for a small number of inevaluable patients, the accrual ceiling will be set at 27 patients.

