10.4.2 Analysis of the Primary Endpoints

The toxicity grades and types per patient will be tabulated and reported.

The fraction of evaluable patients who experience a response (PR+CR) will be reported along with a 95% two-sided confidence interval.

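### The co-primary safety analysis has two conflicting populations (both agents in 10.2, either agent in 10.3); a smaller point is that the both-agents efficacy set in 10.3 is mislabelled intention to treat

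*Combined protocol and SAP*

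**What the plan says.** **Safety.** Section 10.1 lists safety and tolerability as the first of two primary objectives. Section 10.2 states: "The safety and tolerability will be evaluated on all patients who receive at least one dose of both agents". Section 10.3 instead takes consenting, enrolled subjects "who receive at least one dose of either agent will be included in the safety evaluations". Section 10.4.2 tabulates toxicity grades and types per patient, and 10.4.4 tabulates the fraction of patients with each toxicity. Neither says which patients form the denominator.

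**Efficacy.** The single paragraph of section 10.3 opens with the label intention to treat and then adds that "those who receive a least one dose of both agents will be included in the efficacy evaluations". The objective in 10.1 is best overall response "of combined treatment of VB-111 and nivolumab in patients with refractory, metastatic CRC". Section 10.4.2 reads: "The fraction of evaluable patients who experience a response (PR+CR) will be reported". Sections 10.2, 10.4.1 and 10.4.6 also count evaluable patients. No section defines that word or says that it means the 10.3 efficacy set. On replacement, 10.2 says: "To allow for a small number of inevaluable patients, the accrual ceiling will be set at 27 patients".

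**Timing.** VB-111 is given on day 1 of cycle 1 (section 3.2.1). Cycles last 2 weeks, and "nivolumab will be administered every 2 weeks starting on cycle 2 day 1" (section 3.1). Every patient therefore passes through a period of about 2 weeks on VB-111 alone.

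**The concern.** The two safety definitions stand in adjacent sections of the current text and cannot both apply. They differ only for patients who receive one agent and never the other. Given the staggered start, those are mainly patients who leave treatment after VB-111 and before the first nivolumab dose, for example by withdrawal, death or myocarditis (section 3.3 ends all study treatment for myocarditis). Some of these exits may themselves be toxicity. Under the 10.2 wording, those patients would be missing from the results for a primary objective, and nothing in 10.4 settles which wording governs.

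The efficacy question is milder. A set that depends on reaching a second drug 2 weeks after the first is not an intention-to-treat set. Patients left out of it are unlikely to be responders; section 10.2 itself says that "patients with mCRC who have failed other treatments are unlikely to experience a clinical response to a single agent". Leaving them out can therefore be expected to move the response rate upward if it moves it at all, and no rate in all treated patients is planned beside it.

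**Working it through.** **Inputs.** From section 10.2: p0 = 0.05, p1 = 0.25, stage 1 of 9 evaluable patients (stop at 0 responses), 24 evaluable in total, success at 3 or more responses, accrual ceiling 27. The ceiling leaves 27 − 24 = 3 spare places. The documents give no rate of loss before nivolumab, so k = 1, 2 or 3 VB-111-only patients is an **assumption**; k may be 0.

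**Step 1: reproduce the plan's design.**
- Early termination at p0: 0.95^9 = 0.630, the stated 63.0%.
- Probability of success = sum over x1 ≥ 1 of Bin(x1; 9, p) × P(X2 ≥ 3 − x1), with X2 ~ Bin(15, p).
- p = 0.05 gives 0.0931; p = 0.25 gives 0.9028.

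Type I error is 9.3% and power 90.3%, both within the planned limits. The design arithmetic is sound.

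**Step 2: safety, the two denominators.** If t of the 24 both-agents patients and u of the k VB-111-only patients have a given toxicity, 10.2 reports t/24 and 10.3 reports (t + u)/(24 + k). The extreme case is t = 0, u = k (exact Clopper-Pearson 95% intervals):

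| k | 10.2 wording | 10.3 wording |
|---|---|---|
| 1 | 0/24 = 0% (0 to 14.2%) | 1/25 = 4.0% (0.1 to 20.4%) |
| 2 | 0/24 = 0% (0 to 14.2%) | 2/26 = 7.7% (0.9 to 25.1%) |
| 3 | 0/24 = 0% (0 to 14.2%) | 3/27 = 11.1% (2.4 to 29.2%) |

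A less extreme example, also assumed, is t = 2 and u = k = 1: 2/24 = 8.3% against 3/25 = 12.0%.

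**Step 3: response, both-agents set against all treated.** With r responders and k excluded non-responders, r/24 becomes r/(24 + k):

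| Responders | r/24 | k = 1 | k = 2 | k = 3 |
|---|---|---|---|---|
| 3 | 12.5% (2.7 to 32.4%) | 12.0% | 11.5% | 11.1% (2.4 to 29.2%) |
| 6 | 25.0% (9.8 to 46.7%) | 24.0% | 23.1% | 22.2% (8.6 to 42.3%) |

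The largest shifts shown are 12.5 − 11.1 = 1.4 points and 25.0 − 22.2 = 2.8 points. The four intervals in the table are about 27 to 37 points wide. If the trial stops at 0/9, both rates are 0%.

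**Step 4: does the decision rule change?** No. The 0/9 and 3/24 rules stay on the both-agents set, so the error rates of step 1 stand.

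**The case against.** **The route to exclusion is narrow.** This largely stands. Sections 3.1 and 3.3 let a patient who stops one drug for toxicity continue the other at the investigator's discretion, so stopping VB-111 does not by itself keep a patient from nivolumab. Imaging is every 8 weeks, so few patients should have scan-detected progression in the first 2 weeks. Withdrawal, death and myocarditis remain possible.

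**No safety data are lost.** This is correct. Section 6.1 documents adverse events from day 1 of cycle 1. The conflict concerns who enters the summaries, not what is recorded. A reader might infer that the enrollment halt in section 3.4 is weakened; it is not, because that rule refers to events within 30 days of receiving investigational agent and is tied to neither analysis set.

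**The 0/24 contrast is unrealistic.** This is fair. The 24 others would normally also have received the cycle 1 VB-111 dose, so a toxicity confined to the VB-111-only patients would be unusual. The contrast is a bound, not a forecast.

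**Section 10.3 already implies what evaluable means.** This is reasonable: the populations section says who enters the efficacy evaluations. The link is nevertheless unstated, and the text does not say how a both-agents patient without a post-baseline scan is counted.

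**The both-agents set is legitimate.** This stands in full, because the objective is response to the combination.

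Two stronger readings should be resisted. A reader might infer that the response rate will be published as an intention-to-treat result, but 10.4.1 and 10.4.2 describe it as a fraction of evaluable patients. A reader might also infer that type I error exceeds 10%. That requires redefining the null as a 5% rate in all treated patients, whereas 10.2 frames its target for patients treated with the combination.

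**Conclusion.** The safety-set conflict is an error as written: two incompatible populations for a co-primary objective, with no denominator in 10.4 to decide between them. Its practical size depends on how many patients stop after VB-111 alone. That number is not given and may be zero. With 1 to 3 such patients, the bound is a toxicity reported as 0/24 instead of 4.0% to 11.1%.

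The efficacy part is a cheap improvement, not a flaw in the design. The label is wrong, the link between the set and the word evaluable is left implicit, and a supplementary all-treated rate would be informative. In the cases shown the shift is at most 1.4 points at 3 responders and 2.8 points at 6, if every excluded patient is a non-responder. That is an assumption: section 3.5 continues imaging for patients who leave treatment for reasons other than progression, so a response could still be recorded.

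**What to change.** 1. **Section 10.2:** define the safety set as patients with at least one dose of either agent, matching 10.3, and name that denominator in 10.4.2 and 10.4.4.
2. **Section 10.3:** rename the both-agents set *response-evaluable*, state that it is the evaluable set of 10.2 and 10.4, and count a both-agents patient with no documented response as a non-responder. Keep this set for the 0/9 and 3/24 rules.
3. **Section 10.4.2:** add, as a supplementary result, the response rate with exact 95% confidence interval in all patients who received any study drug, counting no documented response as non-response.

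The cost is text edits in four sections and one additional proportion, which may come out slightly lower than the response-evaluable rate. No extra patients are needed and the two-stage error rates do not change.

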10.4 STATISTICAL ANALYSES

10.4.1 General Approach

Following a determination of safety and tolerability based on reporting toxicities, the fraction of all evaluable patients who experience a response will be reported along with confidence intervals.

10.4.2 Analysis of the Primary Endpoints

The toxicity grades and types per patient will be tabulated and reported.

The fraction of evaluable patients who experience a response (PR+CR) will be reported along with a 95% two-sided confidence interval.

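### Does a 95% two-sided response interval, with no method named, conflict with a two-stage rule run at one-sided alpha 0.10?

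*Combined protocol and SAP*

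**What the plan says.** Section 10.2 states "This trial will be conducted using a Simon optimal two-stage phase II trial design", intended "to rule out an unacceptably low response rate (CR+PR) of 5"% "in favor of an improved response rate of 25"%. Alpha is defined in one direction ("probability of accepting a poor treatment=0.10") and beta is also 0.10 ("probability of rejecting a good treatment=0.10"). Stage 1 takes 9 evaluable patients and stops if none responds; otherwise accrual goes on to 24. The final rule is a count: "If there were 3 or more of 24 (12.5%) who experienced a response, this would be sufficiently interesting" enough to justify later trials, whereas 1 or 2 responses would not be. Section 10.4.6 repeats that the number of responses among the first 9 governs entry to stage 2.

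The interval appears only under reporting. Section 10.4.1 says that "the fraction of all evaluable patients who experience a response will be reported along with confidence intervals", and section 10.4.2 gives the level: "The fraction of evaluable patients who experience a response (PR+CR) will be reported along with a 95% two-sided confidence interval". Section 10.4.3 uses 95% intervals for median PFS and OS as well. No section names a method for the response interval, plans a p-value, or requires the interval to exclude 5%.

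**The concern.** A one-sided test at 0.10 corresponds to an 80% two-sided interval, because each tail then holds 0.10. A 95% two-sided interval leaves only 0.025 in the lower tail. Test and interval can therefore point in different directions in the same report: 3/24 meets the rule meant to rule out 5%, beside an interval that includes 5%.

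Two further details make it look worse. Matching the level alone would not restore agreement, because the ordinary exact 80% interval at 3/24 also starts just below 5%. And because no method is named, an analyst could in principle choose one after seeing the data. If that choice moved the trial's conclusion, it would be a real defect in the primary efficacy analysis.

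**Working it through.** **Inputs.** From section 10.2: p0 = 0.05, p1 = 0.25, alpha = beta = 0.10, n1 = 9 with a stop at 0 responses, N = 24, success at 3 or more. From section 10.4.2: 95%, two-sided.

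**1. Reproduce the design.** With X1 ~ Bin(9, p) and X2 ~ Bin(15, p),

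P(success) = P(X1=1)·P(X2≥2) + P(X1=2)·P(X2≥1) + P(X1≥3).

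- At 5%: 0.2985 × 0.1710 + 0.0629 × 0.5367 + 0.0084 = 0.0931.
- At 25%: 0.2253 × 0.9198 + 0.3003 × 0.9866 + 0.3993 = 0.9028.
- Early termination at 5%: 0.95^9 = 0.630, as the plan states.

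Both error limits are met.

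**2. Lower limits of the 95% interval.** The exact (Clopper-Pearson) lower limit for x/24 is the 0.025 quantile of Beta(x, 25 − x). The two-stage exact limit is the p at which the two-stage probability of x or more responses equals 0.025.

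| Method | 3/24 | 4/24 | 5/24 |
|---|---|---|---|
| Exact | 2.7% | 4.7% | 7.1% |
| Two-stage exact | 2.9% | 4.9% | 7.3% |
| Jeffreys | 3.6% | 5.9% | 8.4% |
| Agresti-Coull | 3.5% | 6.1% | 8.8% |
| Wilson | 4.3% | 6.7% | 9.2% |
| Wald | below 0 | 1.8% | 4.6% |

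At 3/24 every method contains 5%, so the choice of method is irrelevant there. At 4/24 the methods split. At 5/24 all but Wald exclude 5%, and Wald gives a negative limit at 3/24, which is reason enough not to use it at this sample size.

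**3. An interval matched to the test.** The 80% lower limits at 3/24 are 4.7% (ordinary exact) and 5.2% (two-stage exact). The single-sample probability of 3 or more of 24 at a true 5% is 0.116, against 0.093 for the two-stage design. The difference arises because the single-sample figure ignores the stop at 0/9. Only the two-stage 80% interval agrees with the rule at 3/24. At 4/24 both 80% lower limits clear 5% (7.5% and 7.8%).

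**4. How often the overlap arises.**

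| True rate | P(pass) | P(exactly 3/24) | Share of passes |
|---|---|---|---|
| 5% | 0.093 | 0.067 | 72% |
| 10% | 0.364 | 0.172 | 47% |
| 25% | 0.903 | 0.058 | 6.5% |

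**5. Validity of the obvious default.** Using the ordinary exact 95% interval (n = 9 after a stage 1 stop, n = 24 otherwise) and weighting by the two-stage probabilities, the minimum coverage for true rates from 1% to 50% is 0.9503. Ignoring the two stages does not make the reported interval invalid.

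**6. What the interval decides.** Sections 10.2 and 10.4.6 base both decisions on counts. Putting any row of the table in step 2 into the report leaves both decisions, alpha and power as they were.

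**The case for a change.** The strongest case for a change is that the plan sets out to rule out 5% and says nothing about how the interval relates to that aim. A reader who sees a passed rule beside 2.7% to 32.4% gets no planned explanation. The case is not remote: at a true rate of 10%, the level section 10.2 says it would be desirable to exceed, 17% of all trials and 47% of passing ones end on exactly 3/24. A two-stage p-value (0.093 at 3/24) and a two-stage 80% interval would cost only a few lines.

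The arithmetic stands, and so does the observation that no method is named. The inference does not. A screening test with a deliberately generous alpha and an estimation interval at the conventional level serve different purposes and need not share a level; section 10.4.3 shows that 95% is this plan's general reporting level. Reporting an 80% interval as well would not take the 95% one away, so 5% would still lie inside it at 3/24. The reader would have more numbers and the same decision. The freedom over method is also narrower than it looks: leaving Wald aside, it changes only how 4/24 compares with 5%, and 4/24 passes the rule under every method.

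**Conclusion.** The concern describes the numbers correctly, but it does not show a fault in the plan. The go/no-go rule is a count whose stated error rates reproduce, and the interval is for estimation. An overlap with 5% at the minimum passing count is what alpha 0.10 implies, and it is useful caution about a result of 3/24.

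What remains is an unnamed method. An analyst would sensibly fill that gap with the exact interval, which keeps coverage of at least 0.9503 under this design. A clause naming it and calling it descriptive would be harmless tidying; nothing in the trial depends on it.

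This rests on two assumptions: that the interval is used as sections 10.4.1 and 10.4.2 present it, reported and not used as a criterion for success; and that the final analysis has 24 evaluable patients, or 9 if stage 1 stops the trial.

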10.4.3 Analysis of the Secondary Endpoints

PFS and OS will be determined using the Kaplan-Meier method, and the median PFS and OS will be reported along with 95% confidence intervals.

10.4.4 Safety Analyses

The fraction of patients who experience a toxicity, by grade and type of toxicity, will be tabulated.

10.4.5 Baseline Descriptive Statistics

Baseline demographic characteristics will be reported.

10.4.6 Planned Interim Analysis

As indicated in the two-stage design, the number of responses after 9 evaluable patients have been treated will be noted and will be used to determine if enrollment to the second stage of accrual may proceed.

10.4.7 Planned Exploratory Analysis:

VB-111 adenovector level in the blood and tumor samples of patients treated with VB-111 will be measured by RT-PCR. Results will be analyzed using descriptive statistics including confidence intervals when appropriate. Any statistical tests performed for evaluation of exploratory objective will be done without formal adjustment for multiple comparisons, but in the context of the number of tests performed.

11 COLLABORATIVE AGREEMENTS

11.1 COOPERATIVE RESEARCH AND DEVELOPMENT AGREEMENT (CRADA)

The CRADA #03295 is in place between NCI, NIH and VBL Therapeutics, the manufacturer of VB-111.

12 HUMAN SUBJECTS PROTECTIONS

12.1 RATIONALE FOR SUBJECT SELECTION

This study was designed to include women and minorities but was not designed to measure differences of intervention effects. Males and females will be recruited with no preference to gender. No exclusion to this study will be based on race. Minorities will actively be recruited to participate.

12.2 PARTICIPATION OF CHILDREN

Children (younger than 18 years) will not be included in this protocol due to the limited data on nivolumab and VB-111 in children and the different biology of childhood malignancies.

12.3 PARTICIPATION OF SUBJECTS UNABLE TO GIVE CONSENT

Adults unable to give consent are excluded from enrolling in the protocol. However, re-consent may be necessary and there is a possibility, though unlikely, that subjects could become decisionally impaired. For this reason and because there is a prospect of direct benefit from research participation (**Section Error! Reference source not found.**), all subjects will be offered the opportunity to fill in their wishes for research and care, and assign a substitute decision maker on the “NIH Advance Directive for Health Care and Medical Research Participation” form so that another person can make decisions about their medical care in the event that they become incapacitated or cognitively impaired during the course of the study. Note: The PI or AI will contact the NIH Ability to Consent Assessment Team (ACAT) for evaluation to assess ongoing capacity of the subjects and to identify a LAR, as needed.

Please see section **12.5.1** for consent procedure.

12.4 RISK/BENEFIT ASSESSMENT FOR ALL PARTICIPANTS

12.4.1 Known Potential Risks

The primary risk to patients participating in this research study is from the toxicity of nivolumab and VB-111. Risks of nivolumab are discussed in nivolumab package insert and risks of VB-111 are discussed in section **1.2.5.7** and the current version of VB-111 Investigators Brochure.

Intestinal perforation has been reported as a very rare event possibly associated with the treatment of VB-111 (please, see Investigators Brochure for VB-111).

Intestinal perforation is an uncommon occurrence in colorectal cancer that has been diagnosed and usually undergone surgical resection, adjuvant chemotherapy or treatment for further advanced stages of CRC. Within populations of patients with CRC reported in the literature, those with and intestinal perforation are usually presenting with the disease; this is the first manifestation of the CRC and they usually undergo emergency surgery. Intestinal perforation is not reported in the literature as a common or expected complication seen in patients with diagnosed CRC who have already undergone surgical and systemic treatment as those that will be included in this protocol [[41](#), [42](#)].

We believe that patients with CRC treated on this trial would not be at any higher risk than other populations of cancer patients currently being studied and treated with VB-111.

